- 8) Females of childbearing potential (FCBP) must have a negative pregnancy test at Screening and Baseline. While on investigational product and for at least 28 days after taking the last dose of investigational product, FCBP who engage in activity in which conception is possible must use one of the approved contraceptive options described below:

Option 1: Any one of the following highly effective contraceptive methods: hormonal contraception (oral, injection, implant, transdermal patch, vaginal ring); intrauterine device (IUD); tubal ligation; or partner's vasectomy.

OR

Option 2: Male or female condom (latex condom or nonlatex condom NOT made out of natural [animal] membrane [for example, polyurethane]); PLUS one additional barrier method: (a) diaphragm with spermicide; (b) cervical cap with spermicide; or (c) contraceptive sponge with spermicide.

The female subject's chosen form of contraception must be effective by the time the female subject presents for her Baseline visit (for example, hormonal contraception should be initiated at least 28 days before first spesolimab infusion at Baseline).

Exclusion Criteria:

The presence of any of the following will exclude a subject from enrollment:

- 1) Subject has a persistent or recurring bacterial infection requiring systemic antibiotics, or clinically significant viral or fungal or helminth parasitic infections, within 2 weeks of the Screening Visit. Any treatment of such infections must have been completed at least 2 weeks prior to the Screening Visit and no new/recurrent infections should have occurred prior to the Baseline Visit.
- 2) Subject with current or history of positive human immunodeficiency virus (HIV), or congenital or acquired immunodeficiency (i.e. Common Variable Immunodeficiency [CVID]), hepatitis B or C, or active or untreated latent tuberculosis.
- 3) Subject has clinically significant (as determined by the investigator) renal, hepatic, hematologic, intestinal, endocrine, pulmonary, cardiovascular, neurological, psychiatric, immunologic, or other major uncontrolled diseases that will affect the health of the subject during the study, or interfere with the interpretation of study results. Uncontrolled disease defined as hospitalization within 1 month of screening visit or determined by specialist (rheumatologist, gastroenterologist) consulted prior to study start.
- 4) Subject has presence of acute demyelinating neuropathy

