In the phase 2 trial investigating spesolimab use in GPP, there were no serious adverse events in the spesolimab 900mg intravenous infusion group¹⁵. Serious adverse events reported included: drug reaction with eosinophilia and systemic symptoms, urinary tract infection, drug induced hepatic injury, arthritis, influenza, worsening of chronic plaque psoriasis and squamous cell carcinomas of skin¹⁵. The most common selected adverse reactions occurring in >1% of spesolimab treated individuals in the Effisayil-1 trial when compared to placebo was: asthenia and fatigue, nausea and vomiting, headache, pruritus and prurigo, infusion site hematoma and bruising, urinary tract infection, bacteremia, bacteriuria, cellulitis, herpes dermatitis and oral herpes, upper respiratory tract infection, dyspnea, eye edema, and urticaria¹⁴. The most common adverse reactions noted in the package insert for spesolimab are: asthenia and fatigue, nausea and vomiting, headache, pruritus and prurigo, infusion site hematoma and bruising and urinary tract infection¹⁴.

The paragraphs above provide the safety information described in the US PI (spesolimab label in US) according to the FDA approval process. However, Boehringer-Ingelheim’s position concerning the adverse drug reactions of spesolimab in patients with flares of Generalized Pustular Psoriasis is described in the table 1 below:

Table 1 Summary of Adverse Reactions

MedDRA System Organ Class terminology	Spesolimab adverse reactions
Infections and infestations	Urinary tract infection Upper respiratory tract infection
Skin and subcutaneous tissue disorders	Pruritus

General disorders and administration site conditions	Injection site reactions Fatigue
---	---

Moreover, there are some important potential risks still under evaluation for spesolimab which are part of its core Risk Management Plan. These important potential risks are the following:

- **Serious or opportunistic infections**
- **Systemic hypersensitivity reactions**
- **Malignancy**
- **Peripheral Neuropathy**

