- Urine pregnancy test for all female subjects of child-bearing potential to confirm subject is not pregnant
- Collect blood samples for CBC with differential, CMP, and C-reactive protein (CRP), serum cytokine profiling (O-link® inflammatory cytokine panel, IL-1 β , and IL-36 subtypes), Nab, ADA, and Pre- and post dose pharmacokinetics.
- Administer study drug

Spesolimab Treatment Phase

Visits 3 thru 9 (subjects that dose every 4 weeks) or Visits 3 thru 11 (subjects that are switched to every 3 week dosing at Week 8)

- Record concomitant medications (including use of pain medication) and adverse events
- Urine pregnancy test for all female subjects of child-bearing potential to confirm subject is not pregnant
- Patient Pyoderma Gangrenosum Questionnaires and DLQI
- Obtain vital signs
- Standardized clinical photography of target lesion and other PG lesions
- PG clinical assessments (including number/location/measurements of PG lesions and GPG score for target lesion)
- Assess status of associated comorbid conditions (improved, no change, worse)
- Collect blood samples for CBC with differential, CMP, and C-reactive protein (CRP)
- **Only at Week 8 and Week 28 (subjects dosed every 4 weeks) or Week 26 (subjects switched to dosing every 3 weeks):** Nab, ADA, and pre dose pharmacokinetics.
- **Only at Week 16:** serum cytokine profiling (O-link® inflammatory cytokine panel, IL-1 β , and IL-36 subtypes), Nab, ADA, and pre dose pharmacokinetics.
- Administer study drug

Post-Spesolimab Follow-up Phase

Visits 10 thru 13 (subjects dosed every 4 weeks) or Visits 12-15 (subjects switched to dosing every 3 weeks)

Follow-Up Visits at 1 Month, 2 Months, 3 Months and 4 Months Post-Spesolimab Treatment Cessation

- Record concomitant medications (including use of pain medication) and adverse events
- Patient Pyoderma Gangrenosum Questionnaires and DLQI
- Assess status of associated comorbid conditions (improved, same, worse)
- Standardized clinical photography of target lesion and other PG lesions

- PG clinical assessments (including number/location/measurements of PG lesions, and GPG score of target lesion)
- Collect blood for serum cytokine profiling (O-link® inflammatory cytokine panel, IL-1 β , and IL-36 subtypes)
- If subject worsens or sees progression of their PG during the 4- month follow-up period (defined as 1 or more increase in GPG score of target lesion), then patient will be discontinued from the study and started on available, standard PG therapies.

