- is life-threatening, which refers to an event in which the patient was at risk of death at the time of the event; it does not refer to an event that hypothetically might have caused death if more severe,
- requires inpatient hospitalization or prolongation of existing hospitalization
- results in persistent or significant disability or incapacity,
- is a congenital anomaly / birth defect,
- is deemed serious for any other reason if it is an important medical event when based on appropriate medical judgement which may jeopardize the patient and may require medical or surgical intervention to prevent one of the other outcomes listed in the above definitions.

Examples of such events are intensive treatment in an emergency room or at home for allergic bronchospasm, blood dyscrasias or convulsions that do not result in hospitalization or development of dependency or abuse.

Adverse events of Special Interest (AESIs)

The term AESI relates to any specific AE that has been identified at the project level as being of particular concern for prospective safety monitoring and safety assessment within this trial, e.g. the potential for Aes based on knowledge from other compounds in the same class. AESIs need to be reported to the Pharmacovigilance Department of Boehringer Ingelheim within the same timeframe that applies to SAEs.

Patients with AESIs need to be followed up appropriately, regardless of the origin of the laboratory data (e.g. central, local etc.). The Investigator should consider which, if any, concomitant therapies should not be taken during evaluation. Discontinued treatments can be reintroduced per Investigator discretion.

The following are considered as AESIs:

(1) Potential Severe Drug-Induced Liver Injury (DILI)

A hepatic injury is defined by the following alterations of hepatic laboratory parameters after randomisation:

- an elevation of AST (Aspartate Aminotransferase) and/or ALT (Alanine Aminotransferase) ≥ 3 -fold ULN combined with an elevation of total bilirubin ≥ 2 -fold ULN measured in the same blood draw sample, or in samples drawn within 30 days of each other, or,
- aminotransferase (ALT, and/or AST) elevations ≥ 10 -fold ULN.

These laboratory findings constitute a hepatic injury alert and the patients showing these abnormalities need to be followed up according to medical judgement.

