The outcome of the pregnancy associated with the drug exposure during pregnancy must be followed up and reported to the Sponsor's unique entry point on the Pregnancy Monitoring Form for Studies (Part B).

As pregnancy itself is not to be reported as an AE, in the absence of an accompanying SAE and/or AESI, only the Pregnancy Monitoring Form for Studies and not the SAE form is to be completed. If there is an SAE and/or AESI associated with the pregnancy an SAE form must be completed in addition.

STUDY WITHDRAWAL:

In the event a study subject wants to withdraw early from the study for any reason, the subject will be asked to return for an Early Termination visit (see above for procedures).

Table 2: TOTAL VOLUME OF BLOOD COLLECTED DURING THE STUDY:

		Treatment				Follow-Up
Visit	1 Screening	2 Baseline	3, 5, 7, 8, 9	4	6	10-13

Blood + Serum	23	32	15	20	23	23
Total volume	23	23	15	20	23	23

The total estimated blood volume is between 15 and 23 mL per month during treatment, and 23 mL per month during Follow-Up period. Additional volumes may be required for repeat testing or as part of unscheduled visits.

DISCONTINUATION OF TREATMENT AND WITHDRAWAL OF SUBJECTS:

The reasons why a subject may discontinue or be withdrawn from the study by the investigator include, but are not limited to the following: subject request, protocol violation, loss to follow up, subject non-compliance, significant worsening of subject's disease, study termination by investigators, and a confirmed grade 3 or higher adverse event (using Common Terminology Criteria for Adverse Events), which is suspected to be related to test article administration. Subjects that elect to withdraw from the trial due to lack of efficacy and/or exacerbation of disease will undergo an Early Termination visit (see Procedure Section and Schedule of Events)

Stopping Rules

Patients will be permanently discontinued from study treatment in the event of:

- Anaphylactic reaction or other severe systemic reaction to study drug injection
- Pregnancy at any time during the study period
- Diagnosis of a malignancy during study, excluding carcinoma in situ of the cervix, or squamous or basal cell carcinoma of the skin
- Treatment with any prohibited concomitant medication or procedure
- Any infection that is opportunistic, whose nature or course may suggest an immunocompromised status

Study drug dosing may be temporarily suspended in the event of:

- Intercurrent illnesses or major surgery

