Data including the patient info, demographics, clinical scores will be stored in password-protected files that will be shared only with investigators and a biostatistical team, if necessary. Data will be stored on secure Mount Sinai servers that may only be accessed by investigators listed on this protocol.

Analysis of Safety and Tolerability

Safety will be evaluated by tabulations of adverse events (AEs) and will be presented with descriptive statistics at each visit. AEs will be coded using the CTCAE, Common Terminology Criteria for Adverse Events, V 4.0 and MedDRA. The number and percentage of subjects/lesions experiencing an AE/SAE will be stratified by system organ class, or a preferred term, and/or severity of the adverse event, and recorded and tabulated overall by each sub-strata. Each subject will be counted only once within a system organ class or a preferred term using the adverse events with the highest severity within each category. All information pertaining to adverse events noted during the study will be listed by subject, detailing verbatim given by the investigator, preferred term, system organ class, date of onset, date of resolution, severity, and relationship to treatment. A tabulation of AEs will be provided by subject.

Table 3. Schedule of Events Q4 Week Dosing Through Week 28

Visit Week	(Up to -28 Days before Baseline)	0	4	8	12	16	20	24	28	4 wk post-spesolimab last dose	8 wk post-spesolimab last dose	12 wk post-spesolimab last dose	16 wk post-spesolimab last dose		
Visit #	1	2	3	4	5	6	7	8	9	10	11	12	13		
Visit Type	Screening	Baseline	TX	TX	TX	TX	TX	TX	TX	F/Up	F/Up	F/Up	F/Up	Early Term (ET)	Additional Treatment Visits
Informed Consent	X														
Inclusion/Exclusion Criteria	X	X													
Demographics/Medical Hx ¹	X														
Limited Physical Exam	X	X													
Vitals ²	X	X	X	X	X	X	X	X	X					X	X
Serum Preg Test	X														
Urine Preg Test		X	X	X	X	X	X	X	X					X	X
CBC w/differential, CMP and CRP	X	X	X	X	X	X	X	X	X					X	X
Screening for TB (Quantiferon Gold, or PPD), HIV, HepB and HepC	X														
PG Clinical Assessments (including number location and measurements)	X	X	X	X	X	X	X	X	X	X	X	X	X	X	X
Global PG (GPG) Severity Score	X	X	X	X	X	X	X	X	X	X	X	X	X	X	X
Subject PG Questionnaire DLQI		X	X	X	X	X	X	X	X	X	X	X	X	X	X

Visit Week	(Up to -28 Days before Baseline)	0	4	8	12	16	20	24	28	4 wk post-spesolimab last dose	8 wk post-spesolimab last dose	12 wk post-spesolimab last dose	16 wk post-spesolimab last dose		

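### Subjects who complete treatment have no scheduled CBC, CMP or CRP after the day of the last infusion, so late asymptomatic laboratory abnormalities would not be looked for systematically

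*Combined protocol and SAP*

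**What the plan says.** **Treatment visits.** The Spesolimab Treatment Phase list in Procedures asks sites at every visit to "Collect blood samples for CBC with differential, CMP, and C-reactive protein (CRP"), and places this before drug administration.

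**Follow-up visits.** The Post-Spesolimab Follow-up Phase covers "Follow-Up Visits at 1 Month, 2 Months, 3 Months and 4 Months Post-Spesolimab Treatment Cessation". Its only blood test is "Collect blood for serum cytokine profiling".

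**Schedules.** The row "CBC w/differential, CMP and CRP" is marked at Visits 1 to 9 in Table 3 and at Visits 1 to 11 in Table 4. It is blank at the four follow-up visits in each table (10 to 13, and 12 to 15). It is marked again at Early Termination and at additional treatment visits. Text and tables agree.

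**Events of special interest.** The first AESI is potential severe drug-induced liver injury, defined by laboratory values. It requires AST or ALT of at least 3 times the upper limit of normal (ULN) with bilirubin of at least 2 times ULN, "measured in the same blood draw sample, or in samples drawn within 30 days of each other", or aminotransferases of at least 10 times ULN. The section on SAE reporting to the drug supplier runs the SAE and AESI window from consent to the end of protocol follow-up.

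**Background risk.** Potential Risks of Spesolimab names "drug reaction with eosinophilia and systemic symptoms, urinary tract infection, drug induced hepatic injury" among the serious adverse events reported in the earlier psoriasis trial.

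**Blood volume.** The text under Table 2 gives "23 mL per month during Follow-Up period".

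**The concern.** During treatment, any laboratory effect of an infusion can be seen in the panel taken at the next visit. The last infusion has no next panel for a subject who completes treatment. The plan nevertheless keeps the reporting window for a laboratory-defined AESI open for another 16 weeks and draws blood four times in that window.

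What is at stake is the reading of the post-treatment safety data. If ALT, AST and bilirubin are not measured on a schedule, a count of zero hepatic AESIs in follow-up mainly reflects how rarely anyone looked. The few values that do exist would come from subjects who had symptoms, who left early, or whose investigator chose to test. That is a selected group with no clear denominator.

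**Working it through.** The plan states no figure for this point, so the check compares the schedule with the reporting window and adds some simple arithmetic.

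**1. Panels scheduled in follow-up (Tables 3 and 4).** Four-weekly schedule: 0 of 4 visits. Switched schedule: 0 of 4 visits.

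**2. Share of on-study time without a scheduled panel, for completers.** Inputs: last infusion at Week 28 or Week 26, and follow-up to 16 weeks after the last dose.
- Four-weekly: 16 / (28 + 16) = 16/44 = 36%.
- Switched: 16 / (26 + 16) = 16/42 = 38%.
- Extended to the 52-week maximum in Procedures, with the same follow-up afterwards: 16 / (52 + 16) = 16/68 = 24%. Additional treatment visits carry the panel, so the gap still begins at the last of them.

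**3. Infusions with no later scheduled panel.** The last one only: 1 of 8 (12.5%) on the four-weekly schedule, 1 of 9 (11%) on the switched schedule.

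**4. The AESI's own pairing rule.** Suppose that ALT on the day of the last infusion is at least 3 but below 10 times ULN, and bilirubin is below 2 times ULN. That is not yet an alert. A bilirubin value within 30 days could complete the definition. The first follow-up visit falls 4 × 7 = 28 days later, inside that limit, and blood is drawn there, but no CMP is scheduled.

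**5. Would the panel fit the stated blood volume?** Table 2 does not break volumes down by test. Assume that volumes add, and take the Table 3 visit content:
- CBC, CMP and CRP only (for example Visit 3): 15 mL.
- Adding pharmacokinetics and antibodies (Visit 4): 20 − 15 = 5 mL.
- Adding cytokines (Visit 6): 23 − 20 = 3 mL.
- Panel plus cytokines at follow-up: 15 + 3 = 18 mL, within 23 mL.
- Cytokines alone: 3 mL, or 3 + 10 = 13 mL if the reserved 10 mL aliquot is counted. Neither explains 23 mL.
- Panel, cytokines and a separate 10 mL aliquot: 18 + 10 = 28 mL, which is 5 mL above the stated volume.

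The additive assumption is shaky. Table 2 puts Visit 9 in the 15 mL group although Table 3 marks pharmacokinetics and antibodies there, and it gives both 32 and 23 mL for Baseline. So the panel may fit within the stated volume, but the documents do not settle it.

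**The case against.** A reader might infer that nobody has a safety laboratory test after the last infusion, or that late toxicity cannot be detected at all. The documents do not support either reading. The Early Termination visit includes CBC, CMP and CRP, so some subjects who leave during follow-up would have them. Clinical symptoms of hepatic injury call for ALT, AST and bilirubin, in an unscheduled test if necessary. The Safety Evaluation section allows extra evaluations when clinically indicated or at the investigator's discretion. Adverse events are recorded at every follow-up visit.

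The risk evidence is also limited. The same background section reports no serious adverse events in the 900 mg intravenous group, a statement that sits awkwardly beside its own list of events. The two DRESS cases were scored as no DRESS and possible DRESS. Hepatic injury appears neither in Table 1 nor among the four important potential risks. The documents give no half-life or onset time that points to liver toxicity first appearing after the last dose. A completer on the four-weekly schedule already has seven panels after dosing began (Weeks 4 to 28). The 36% and 38% measure calendar time, not risk.

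A reader might also extend the point to pregnancy testing, since contraception is required "While on investigational product and for at least 28 days after taking the last dose of investigational product" while no urine test is scheduled for completers after the last infusion. That does not hold up. The criterion sets a duration of contraception, not of testing, the duty to report a pregnancy does not depend on a scheduled test, and the amendment log records that follow-up pregnancy tests were removed on purpose.

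These objections narrow the point but do not remove it. Symptom-prompted testing misses asymptomatic abnormalities by construction, and discretionary testing is not standardised. Early Termination samples come only from subjects who leave, some of them because their disease worsened. The protocol itself gives hepatic injury AESI status, whatever the strength of the background evidence.

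**Conclusion.** The point stands for subjects who complete treatment. They have no routine CBC, CMP or CRP scheduled after the day of the last infusion, and the 16 weeks of follow-up have none: 36% of on-study time on the four-weekly schedule, 38% on the switched schedule, and 24% if treatment runs to the 52-week maximum. Asymptomatic late abnormalities in these subjects would not be detected systematically, and an absence of laboratory-defined AESIs in follow-up would be largely uninformative.

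This rests on the procedures list and both schedules meaning what they say. If the 23 mL in Table 2 was meant to include the safety panel, the fault is instead an omission from the list and the tables, and the same edit cures it. No efficacy endpoint or analysis is affected. The change should be made, because it is specific and cheap and it alters what the trial can say about post-treatment safety.

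**What to change.** In the Post-Spesolimab Follow-up Phase list and in Tables 3 and 4, add CBC with differential, CMP and CRP to the blood already drawn, at least at the first follow-up visit (4 weeks after the last dose) and preferably also at the last (16 weeks). Reconcile Table 2 by breaking the follow-up volume down by test. If the omission is deliberate, say so, and report with any follow-up AESI count how many subjects had a liver test after the last infusion.

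The cost is routine laboratory fees for at most 2 × 20 = 40 panels if all 20 subjects complete follow-up, together with the wording and table marks. No extra visit or venepuncture is needed. The draw may have to be slightly larger, depending on what the 23 mL already covers.
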